16.0 Statistical Considerations and Methodology**16.1 Overview**

This randomized study is pilot in nature insofar as its main goal is to provide preliminary data to put in place the groundwork for a much larger, definitive study. The primary aim of the current study is to compare the time-to-quality of life (QOL) improvement from baseline in postoperative gynecological cancer patients who are receiving oral SBI vs. placebo. If this trial can provide preliminary evidence that oral SBI significantly improves the time-to-QOL improvement as compared to placebo, further study would be warranted to determine whether the administration of oral SBI shortens the time-to-chemotherapy administration post-operatively in ovarian cancer patients. In addition to time-to-QOL improvement, this trial will also compare adverse event rates, complication rates, QOL from validated QOL tools, and intervention compliance between patients receiving oral SBI vs. placebo.

- 16.11 **Primary Endpoint and Statistical Design:** To compare the time-to-QOL improvement from baseline in postoperative gynecological cancer patients who are receiving oral SBI vs. placebo.

Final Analysis:

The primary goal of this trial is to compare the oral SBI arm (experimental) to the placebo arm (standard), where the alternative hypothesis is that the experimental arm has a shorter time to QOL improvement from baseline as compared to the standard arm. For this primary endpoint, the total score of the 14-item Postoperative Quality of Life (PQL) tool [15] will be used, where the total score could range from 0 to 140 (0 being the worst and 140 being the best). These scores will be converted to the percentage scale, where a score of 140 will

be converted to 100 and a score of 0 will remain as 0. This QOL will be measured weekly for the entire 12 week length of the study and at the end of the intervention. QOL improvement will be defined as at least a 10 point increase in the QOL score from baseline, on the percentage scale. This 10 point change represents a clinically meaningful improvement in QOL based on work done by Jeff Sloan [17]. The date at which the QOL score is first known to increase by at least 10 from baseline (on the 100 point scale), will be considered the event date for the purpose of analysis. Patients without at least a 10 point increase in QOL from baseline, will be censored on their last QOL evaluation date up to a maximum of 12 weeks. We will enter a total of 70 evaluable patients (35 per arm) using a 1:1 randomization scheme. The primary analysis will be a comparison of oral SBI vs. placebo using a two-sided log-rank test between the 2 Kaplan-Meier curves [18]. This analysis will take place after an approximate 16 month accrual period, and after 66 total events across both arms combined (which should happen after about 12 weeks of follow-up in all evaluable patients). Additionally, we assume a constant accrual rate over the course of the study, and that no patients will drop-out of the study, since historically the lost to follow-up rate is <1%. To determine the appropriate sample size of 35 evaluable patients per arm, we assumed exponential survival and that the median time-to-QOL improvement is around 3 weeks in the oral SBI arm and 6 weeks in the placebo arm (HR=2). This hazard ratio is based on our institution's data which shows that patients often begin postoperative chemotherapy 6 weeks after surgery. These assumptions yield 80% power to detect a significant difference between the arms using a 2-sided log-rank test at alpha=0.05. All patients who meet the eligibility criteria, sign the consent form, and are randomized, will be considered evaluable for this endpoint. All eligible patients will be followed a maximum of 12 weeks. If the 2-sided log-rank test p-value is < 0.05 showing significantly shortened time-to-QOL improvement in the oral SBI arm as compared to placebo, further study will be warranted. Of course, any final decisions will be based on all primary and secondary endpoints.

- 16.2 Sample Size: The study design to be utilized is fully described in Section 16.11 (see above). There will be 35 evaluable patients randomized to each arm of this study. We anticipate accruing an additional 15 patients to each arm to account for ineligibility, cancellation, major intervention violation, or other reasons. Therefore, maximum accrual is 100 patients (50 per arm).
- 16.3 Accrual Time and Study Duration: The anticipated accrual rate is approximately 4-5 patients per month. Therefore, the accrual period for this randomized Pilot study is expected to be around 24 months. The final analysis can begin approximately 28 months after the trial begins, i.e., as soon as the last patient registered has been observed for 4 months.
- 16.4 Other Considerations: Adverse events as well as scientific discoveries or changes in standard care will be taken into account in any decision to terminate the study.

16.5 Data & Safety Monitoring:

16.51 The principal investigator(s) and the study statistician will review the study at least twice a year to identify accrual, adverse event, and any endpoint problems that might be developing. The trial is monitored continually by the study team who are notified of every grade 4 and 5 event in real time. The Mayo Clinic Cancer Center (MCCC) Data Safety Monitoring Board (DSMB) is responsible for reviewing accrual and safety data for this trial at least twice a year, based on reports provided by the MCCC Statistical Office.

16.52 Adverse Event Stopping Rules: The stopping rules specified below are based on the knowledge available at study development. We note that the Adverse Event Stopping Rule may be adjusted in the event of either (1) the study re-opening to accrual or (2) at any time during the conduct of the trial and in consideration of newly acquired information regarding the adverse event profile of the intervention(s) under investigation. The study team may choose to suspend accrual because of unexpected adverse event profiles that have not crossed the specified rule below. CTCAE v4.0 will be used to determine grading for these stopping rules.

We expect about 10% of patients to experience grade 3 or worse adverse events (at least possibly related to the study intervention). In addition, we expect less than 1% of patients to experience a Grade 5 adverse event, at least possibly related to the study intervention. Accrual will be temporarily suspended to this study if at any time we observe adverse events that satisfy any of the following within each arm separately (i.e. if any of the following occur in arm A or arm B, we will suspend accrual to the trial):

- If at any time 4 or more in the first 20 treated patients (or 20% or more after the first 20) experience a Grade 3 or worse adverse event (possibly, probably, or definitely related to the intervention).
- If at any time, 1 patient experiences a grade 5 adverse event (possibly, probably, or definitely related to the intervention).

We note that we will review all Grade 5 adverse events on a case-by-case basis as well (regardless of attribution), and may suspend accrual after just one Grade 5 event, if we feel it is necessary for patient safety.

16.6 Definitions and Analyses of Secondary Endpoints: All these endpoints will be assessed individually and will also be compared between the 2 arms. Monthly phone calls may be used to collect the secondary endpoint information for each patient, including adverse events, surgical complications, and other data (e.g. patient reported weight, intervention compliance, etc.). We will be assessing, reporting on, and potentially analyzing all the data collected from these monthly telephone calls.

16.61 Adverse Events: All eligible patients who have initiated therapy will be considered evaluable for adverse event analyses. The maximum grade for each type of adverse event will be recorded for each patient up to 16 weeks post-randomization (12 weeks of intervention + 1 month post-intervention observation timepoint), and frequency tables will be reviewed to determine adverse event

patterns. The overall adverse event rates for grade 2 or higher adverse events, will be compared using Chi-Square or Fisher's Exact tests. In addition, the surgical complication rates (up to 1 month post-surgery) will also be compared between the 2 arms using Chi-Square or Fisher's Exact tests.

16.62 **Intervention Compliance:** Intervention compliance will be assessed using the Compliance Questionnaire in Appendix V. The frequency and percentage for each Compliance Questionnaire category will be summarized descriptively by cycle and by intervention arm. In addition, cycle by cycle compliance data will be compared between the 2 arms using a Chi-square test.

16.63 **Quality of Life:** QOL will be measured with 3 QOL tools. For the primary endpoint, the total score from the 14-item Postoperative Quality of Life (PQL) tool [15] (Appendix II) will be used (16.11). As a secondary analysis, all 14 of the individual items from the PQL tool (Appendix II), along with the 4 additional items after the PQL questions (Appendix II) will be analyzed and compared between the 2 intervention arms. In addition, the time-to-QOL improvement will be compared between the 2 arms for any increase (> 0) from baseline for the total score from the PQL tool. This will be done descriptively, and using a Kaplan-Meier analysis [18], where any increase in the QOL from baseline will represent an event. QOL will also be measured using the Uniscale (Appendix III), and the previously-validated Symptom Distress Scale (SDS; Appendix IV). These QOL tools will measure QOL at baseline, every week up to 12 weeks post-randomization, and at the end of intervention. Differences between post-randomization and baseline QOL scores will be analyzed and compared between the 2 arms using a Wilcoxon Rank-sum test. Also, other graphical and statistical methods will be used to compare the QOL and time-to-QOL improvement between the 2 arms. As an exploratory analysis, we will also collect QOL data on patients who do not start intervention/placebo or discontinue intervention/placebo early and are willing to be followed per the test schedule (Section 4). This analysis will be descriptive in nature to see if these patients have a poorer QOL than patients who stay on study.

16.64 **Translational Component:** The hypothesis is that oral SBI will improve postoperative recovery. However, we know of no biomarkers indicative of postoperative recovery. Hence in an exploratory manner, we will measure a host of candidate biomarkers. This study will include serial assessment at baseline, at a mid-way timepoint, and at the end of the intervention intervention. The differences between biomarker values over time will be compared between the 2 intervention arms using a Wilcoxon Rank-sum test. In addition, other graphical and statistical methods will be used to compare the data over time between oral SBI and placebo. All these analyses will be considered hypothesis-generating.

16.7 **Inclusion of Women and Minorities**

16.71 This study will be available to all eligible patients, regardless of race, or ethnic origin.

16.72 There is no information currently available regarding differential effects of this regimen in subsets defined by race, or ethnicity, and there is no reason to expect such differences to exist. Therefore, although the planned analysis will, as

always, look for differences in intervention effect based on racial groupings, the sample size is not increased in order to provide additional power for subset analyses.

16.73 The geographical region served by the Mayo Clinic has a population which includes approximately 5% minorities. We expect about 5% of patients will be classified as minorities by race and all will be women. Expected sizes of racial subsets are shown in the following table:

Accrual Estimates by Ethnicity/Race

Ethnic Category	Sex/Gender			
	Females	Males	Unknown	Total
Hispanic or Latino	0	0	0	0
Not Hispanic or Latino	100	0	0	100
Ethnic Category: Total of all subjects	100	0	0	100
Racial Category				
American Indian or Alaskan Native	0	0	0	0
Asian	2	0	0	2
Black or African American	3	0	0	3
Native Hawaiian or other Pacific Islander	0	0	0	0
White	95	0	0	95
Racial Category: Total of all subjects	100	0	0	100

Ethnic Categories: **Hispanic or Latino** – a person of Cuban, Mexican, Puerto Rican, South or Central American, or other Spanish culture or origin, regardless of race. The term “Spanish origin” can also be used in addition to “Hispanic or Latino.”

- **Not Hispanic or Latino**

Racial Categories: **American Indian or Alaskan Native** – a person having origins in any of the original peoples of North, Central, or South America, and who maintains tribal affiliations or community attachment.

Asian – a person having origins in any of the original peoples of the Far East, Southeast Asia, or the Indian subcontinent including, for example, Cambodia, China, India, Japan, Korea, Malaysia, Pakistan, the Philippine Islands, Thailand, and Vietnam. (Note: Individuals from the Philippine Islands have been recorded as Pacific Islanders in previous data collection strategies.)

Black or African American – a person having origins in any of the black racial groups of Africa. Terms such as “Haitian” or “Negro” can be used in addition to “Black or African American.”

Native Hawaiian or other Pacific Islander – a person having origins in any of the original peoples of Hawaii, Guam, Samoa, or other Pacific Islands.

White – a person having origins in any of the original peoples of Europe, the Middle East, or North Africa.

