5.0 Stratification Factors

- 5.1 Patient age: ≥ 65 years vs. < 65 years
- 5.2 Splenectomy and/or rectosigmoid resection: yes vs. no
- 5.3 Optimally debulked cancer (complete nodal and omental removal, as appropriate, with <1 cm of residual tumor, if appropriate): yes vs. no
- 5.4 Cancer type: ovarian vs. endometrial vs. other
- 5.5 Open laparotomy vs. laparoscopic surgery

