6.2 Randomization Procedures

6.21 The factors defined in Section 5.0 will be used as stratification factors.

6.22 After the patient has been registered into the study, the values of the stratification factors will be recorded, and the patient will be assigned to one of the following intervention groups using the Pocock and Simon dynamic allocation procedure which balances the marginal distributions of the stratification factors between the intervention groups [16].

- Oral Serum Bovine Immunoglobulin (SBI)
- Placebo

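### The primary log-rank test is unstratified although allocation is minimised on five factors; it stays valid, but it could lose power if surgical approach strongly predicts recovery

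*Combined protocol and SAP*

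**What the plan says.** Section 5.0 lists five factors: age, splenectomy and/or rectosigmoid resection, optimal debulking, cancer type (three levels), and "Open laparotomy vs. laparoscopic surgery". It gives no reason for the choice. Section 6.22 assigns patients "using the Pocock and Simon dynamic allocation procedure which balances the marginal distributions of the stratification factors between the intervention groups".

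The primary analysis in Section 16.11 is: "The primary analysis will be a comparison of oral SBI vs. placebo using a two-sided log-rank test between the 2 Kaplan-Meier curves". No strata, covariates or adjusted sensitivity analysis are named, and no hazard ratio with a confidence interval is planned for this endpoint. The sample size rests on the same plain test: "These assumptions yield 80% power to detect a significant difference between the arms" "using a 2-sided log-rank test at alpha=0.05", with 35 evaluable patients per arm and analysis "after 66 total events across both arms combined".

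The nearest wording elsewhere is in 16.63. It allows further unspecified graphical and statistical comparisons of QOL and of time to improvement. It sits under the secondary endpoints and names no factor.

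**The concern.** Minimisation makes the arms more alike on the chosen factors than chance would. A test that ignores those factors still allows for chance imbalance in them. If a factor is prognostic, the test's null variance is then too large, so it rejects too seldom under the null and has less power under the alternative. If no factor is prognostic, nothing is lost.

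Power is what is at stake. Section 16.11 links further study to p < 0.05 on this test, although final decisions are to weigh all endpoints. The trial has 70 evaluable patients and little slack. The factor values are already recorded at randomisation, so using one of them needs no new data.

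**Working it through.** **The plan's own figure.** Inputs from 16.11: medians of 3 and 6 weeks (HR 2), two-sided alpha 0.05, 80% power, 1:1 allocation.

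- Schoenfeld events: 4 × (1.960 + 0.842)² / (ln 2)² = 4 × 7.85 / 0.480 = 65.4, so 66.
- Power at 66 events: Φ(√66 × 0.693 / 2 − 1.960) = Φ(0.856) = 80.4%.

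Both stated figures reproduce for the unstratified test.

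**Baseline for the comparison.** With a 12-week cap, the expected event proportions are 1 − 0.5^(12/3) = 0.9375 and 1 − 0.5^(12/6) = 0.75. Thus 35 × (0.9375 + 0.75) = 59 events, and power is Φ(√59.06 × 0.693 / 2 − 1.960) = 75.9%. The simulated powers below therefore start near 75% and not 80%. That shortfall is a separate matter.

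**Simulations.** All use 70 patients, a treatment HR of 2 within levels of approach and a 12-week cap. Prognostic strengths and factor prevalences are assumptions.

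- A: minimisation on five factors (biased coin 0.8), continuous event times, 3,000 runs per setting. Strength was coded as HR 1.5, 2 and 3, shown beside the roughly reciprocal values 0.67, 0.5 and 0.35.
- B: minimisation on approach only, 60% open surgery, weekly event times, 2,500 runs.
- C: minimisation on five factors, weekly event times.

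Power (%), plain log-rank / log-rank stratified by approach, with the gain in points:

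| HR for approach | A | B | C |
|---|---|---|---|
| 1 (not prognostic) | 74.6 / 73.2 (−1.4) | 76.6 / 76.2 (−0.4) | 75.9 / 75.4 (−0.5) |
| 0.8 | – | 74.2 / 74.0 (−0.2) | – |
| 0.67 | 74.9 / 75.6 (+0.7) | 74.6 / 75.3 (+0.7) | 72.8 / 74.0 (+1.2) |
| 0.5 | 69.7 / 74.4 (+4.7) | 69.8 / 73.0 (+3.2) | 69.8 / 72.8 (+3.0) |
| 0.35 | 60.7 / 71.5 (+10.8) | 59.1 / 70.4 (+11.3) | 58.5 / 67.3 (+8.8) |

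The Monte Carlo standard error of one power figure at 3,000 runs is about √(0.75 × 0.25 / 3000) = 0.8 points, so gains of about 1 point or less are not material. Rounding A to weekly visits at HR 2 gives 68.9 / 73.5 (+4.6), the same pattern.

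**Type I error of the plain test.** In A with 8,000 runs (standard error √(0.05 × 0.95 / 8000) = 0.24 points) it is 5.2% with no prognostic factor, 4.3% at HR 2 and 3.4% at HR 3. In B it is 5.2% at 0.8 and 4.6% at 0.67. In C it is clearly below 5% only at 0.35 (3.4%). The stratified test in A runs at 5.2% to 5.7%, so its power is slightly flattered.

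**Using more factors.** All five give 2 × 2 × 2 × 3 × 2 = 48 cells, or 70/48 ≈ 1.5 patients per cell. A log-rank test stratified on all 48 has only about 40-43% power. A Cox model with all five as covariates recovers power, but its Wald test ran at about 7% type I error. Stratifying by approach and resection together cost 76.5 − 73.2 = 3.3 points in a further simulation with no prognostic factor.

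**The case against.** The strongest reply is that the plain test is legitimate. Test and sample size match, the stated power reproduces, and any error in size is on the safe side. In a self-described pilot a simple unstratified log-rank test is defensible. All of this stands, and what remains is an efficiency point.

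A reader might infer that the factors were chosen because they predict recovery, so that the test must be conservative. The documents do not support this. Section 5.0 gives no rationale and no prognostic figures. The endpoint is a 10-point rise from the patient's own postoperative baseline, so more extensive surgery might lower that baseline and leave more room to improve. Neither the size nor the direction of the association is known. The stratified test helps in either direction, but only if the association is strong: an HR of 0.5 is as strong as the treatment effect the trial hopes to see.

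A reader might also infer that the unadjusted hazard ratio would pass a biased effect to the next trial. It would not. With a prognostic factor, the marginal hazard ratio lies closer to 1 than the conditional one, but it is a different estimand. Moreover, Section 16.1 describes a follow-on trial of time to chemotherapy in ovarian cancer, which this hazard ratio would not size directly.

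The general wording in 16.63 does not exclude adjusted analyses. It is too unspecific to count as pre-specification for the primary endpoint.

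Finally, stratifying by approach alone leaves four allocation factors unused, and choosing approach is a judgement. That is fair. It is the price of keeping the strata large enough to work.

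**Conclusion.** The point holds as a conditional loss of efficiency. Allocation uses five factors and the primary analysis uses none. The plain test's type I error is at or below 5% within simulation error, and clearly below it only when the factor is strong. The power forgone against a test stratified by approach is about 0-1 point at an HR of 0.67 or weaker, 3-5 points at 0.5 and 9-11 points at 0.35. These sizes rest on assumed prognostic strengths and prevalences, exponential times and the plan's medians. The documents supply none of the prognostic inputs. The change is worth making because it costs almost nothing and must be fixed before unblinding to be credible.

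**What to change.** In 16.11, pre-specify the primary test as a two-sided log-rank test stratified by surgical approach (5.5). Report the hazard ratio and 95% CI from a Cox model stratified by the same factor, so that the estimate matches the test. State how ties are handled, because weekly booklets produce many. Keep the unstratified log-rank test as a sensitivity analysis.

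Do not stratify on all five factors. A Cox model that also adjusts for resection (5.2), the other allocation factors or baseline PQL should be labelled supportive, because it no longer matches the primary test. If a test is taken from such a model, a score, likelihood-ratio or re-randomisation test is preferable to the Wald test. Any split into ovarian and non-ovarian patients should be descriptive only: 59 expected events leave roughly 30 per group if they divide evenly.

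Cost: SAP wording only, with no new data and no change in sample size. If approach is not prognostic, the loss is about 1 point of power (0.4 to 1.4 in the simulations above).

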4.0 Test Schedule

Tests and procedures	Active Monitoring Phase				Observation/crossover (ends after 16 weeks of total study participation)
	≤21 days prior to randomization	Day 1 of Cycle 2 and 3 (+/- 3 days)	Weekly from registration for 12 weeks total	At the end of intervention (+/- 3 days)	
Patient assessment (includes weight**)	X				
Adverse event assessment	X	X**		X**	X**
Pregnancy test ¹ (Serum)	X				
Hematology group					
HgB					
WBC	X				
PLT					
ANC					
Chemistry group					
Creatinine	X				
Patient Questionnaire					
Booklets ² , (Appendix 2-5)	X		X	X	X
Blood specimens (see Section 14.0) ^{3,R}	X	X*			

1. For women of childbearing potential only. Must be done ≤7 days prior to registration.
2. Patient questionnaire booklets **must** be used; copies are not acceptable for this submission. Patients are required to fill out the questionnaires at baseline, and weekly for the duration of study participation, (16 weeks total, includes patients who never started therapy).
3. Blood specimens will be collected and submitted at baseline. Kits are required. Baseline blood specimen is to be collected after consent and prior to patient receiving study agent.

R Research funded (see Section 19.0)

*These blood draws are optional but strongly recommended.

** If patient cannot return, this assessment can be done by phone by the study coordinator (includes patient reported weight). However, study questionnaires must be mailed back.

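### The primary log-rank test in 16.11 ignores baseline PQL, the score from which the event is measured; adjusting for it would be a cheap gain in power

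*Combined protocol and SAP*

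**What the plan says.** Section 16.11 sets the event: "QOL improvement will be defined as at least a 10 point increase in the QOL score from baseline, on the percentage scale". The score is the 14-item PQL total, rescaled to 0-100. The test is then: "The primary analysis will be a comparison of oral SBI vs. placebo using a two-sided log-rank test between the 2 Kaplan-Meier curves". No stratum, covariate or supporting Cox model is named.

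The design inputs are in the same section: "We will enter a total of 70 evaluable patients (35 per arm) using a 1:1 randomization scheme"; exponential times with "median time-to-QOL improvement is around 3 weeks in the oral SBI arm and 6 weeks in the placebo arm (HR=2"); analysis "after 66 total events across both arms combined"; and "All eligible patients will be followed a maximum of 12 weeks". On power: "These assumptions yield 80% power to detect a significant difference between the arms using a 2-sided log-rank test at alpha=0.05". A log-rank p-value below 0.05 in favour of SBI is the signal for further study.

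The baseline score will be in hand. Section 4.0 says: "Patients are required to fill out the questionnaires at baseline, and weekly for the duration of study participation". It is not one of the five allocation factors in Section 5.0 (age, splenectomy or rectosigmoid resection, debulking status, cancer type, surgical approach). Section 16.63 uses baseline only through change scores and a Wilcoxon test, and allows further unspecified methods for time to improvement. Nothing commits to adjusting that comparison for baseline PQL.

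**The concern.** The baseline score is part of the outcome, because every later score is judged against it. Two features make some association with time to event plausible. The scale is bounded, so high starters have less room to rise, and above 90 a 10-point rise is impossible. Measurement error at baseline also carries into every later difference, so a baseline that is low by chance will tend to cross the threshold early.

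If baseline does predict time to event, a test that leaves it out has less power than one that uses it. That matters in a trial of 70 evaluable patients whose signal for further work is a single p-value. A useful effect could be missed although the information to detect it had been collected.

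**Working it through.** **1. The plan's own figure.** Inputs from 16.11: hazard ratio 2, two-sided alpha 0.05, power 80%, 1:1 allocation. The Schoenfeld formula gives

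events = 4 × (1.960 + 0.842)² / (ln 2)² = 4 × 7.85 / 0.480 = 65.4, rounded up to 66.

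Power at 66 events = Φ(√66 × 0.693 / 2 − 1.960) = Φ(0.856) = 80.4%. The stated design reproduces.

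**2. Starting point under the 12-week cap.** With medians of 3 and 6 weeks, the event probabilities by week 12 are 1 − 0.5^(12/3) = 0.9375 and 1 − 0.5^(12/6) = 0.75. Expected events from 70 patients are 35 × 0.9375 + 35 × 0.75 = 59.1, and power = Φ(√59.1 × 0.693 / 2 − 1.960) = 75.9%. This is a separate matter. It is noted only because it explains why the unadjusted figures below start near 76% and not 80%.

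**3. Simulation.** Plan inputs: 35 per arm, placebo median 6 weeks, hazard ratio 2, times rounded up to whole weeks, censoring at 12 weeks, two-sided 5%. Assumed input, not in the documents: the strength of the link between baseline and event time, with a higher baseline giving a later event. There were 1,500 trials per setting (Monte Carlo standard error about 1.1 points). Three tests were compared: the unadjusted log-rank, the Cox likelihood-ratio test for treatment with continuous baseline as covariate (Efron ties), and the log-rank stratified by baseline tertile.

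*(a) Each arm's marginal curve held exponential with medians 3 and 6 weeks, as 16.11 assumes:*

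| Correlation of baseline with latent event time | Unadjusted log-rank | Adjusted Cox | Tertile-stratified log-rank |
|---|---|---|---|
| 0 | 76% | 75% | 73% |
| 0.3 | 74% | 78% | 75% |
| 0.5 | 75% | 84% | 81% |
| 0.7 | 76% | 94% | 90% |

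The unadjusted column is flat within simulation error. The adjusted Cox test gains 78 − 74 = 4, 84 − 75 = 9 and 94 − 76 = 18 points. Across repeat runs the unadjusted test gave about 73-77%, adjusted Cox gave 72-75% at correlation 0 and 92-94% at 0.7, and the gains were about 4, 6-9 and 17-20 points.

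*(b) Hazard ratio 2 taken as conditional on baseline:*

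| Log-hazard per SD of baseline | Unadjusted log-rank | Adjusted Cox | Tertile-stratified log-rank |
|---|---|---|---|
| 0 | 75% | 75% | 74% |
| 0.3 | 71% | 74% | 72% |
| 0.5 | 62% | 74% | 68% |
| 0.8 | 49% | 69% | 63% |
| 1.0 | 40% | 68% | 60% |

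Repeat runs gave 62-65% unadjusted against 74-76% adjusted at 0.5, and 40% against 67-68% at 1.0.

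**4. Type I error.** With hazard ratio 1, rejection rates across the three tests were 4.5-6.5%. The adjusted Cox test gave 6.5% in one setting and 4.5% in the other. The standard error is √(0.05 × 0.95 / 1500) = 0.6 points, so a small excess for the Cox test at this sample size is not ruled out.

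**The case against.** The unadjusted log-rank is a valid and conventional primary test, and randomisation protects it. A reader might infer that the result is biased, or that chance imbalance in baseline PQL invalidates it. The documents do not support that. Such imbalance is part of the random error that the test already allows for, and minimisation on the Section 5.0 factors may balance some correlates of postoperative quality of life.

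A reader might also infer that the plan's power collapses, towards 40%. Section 16.11 assumes exponential times with given medians in each arm, which describes the marginal curves. On that reading unadjusted power does not fall with the correlation, and what is lost is a gain not taken. The fall in table (b) needs hazard ratio 2 to hold conditionally on baseline, which the plan does not say.

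The association itself is undocumented, and away from the ceiling even its sign is open. Baseline falls within days of surgery, and low scorers may have had larger operations and recover more slowly, which would work against regression to the mean. With a weak association the gain is small.

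Finally, this is a pilot. Section 16.11 says that final decisions rest on all endpoints, and 16.63 leaves room for other methods. That softens the consequence of a missed p-value, but an unspecified method chosen after unblinding would carry little weight.

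All of this limits the size of the point. None of it supplies a reason to leave the baseline score out.

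**Conclusion.** The point holds as a cheap improvement. The primary test makes no use of a score that defines the event and is already collected. The cost is efficiency only. On the plan's marginal assumptions, adjustment for continuous baseline PQL changes power by about −1 point at correlation 0, and adds about 4 points at 0.3, 6-9 at 0.5 and 17-20 at 0.7. If hazard ratio 2 is conditional on baseline, the gap is about 11-12 points at 0.5 log-hazard per SD and 27-28 at 1.0.

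The size rests on an assumed association that the documents do not give, on 35 per arm (accrual may reach 100 under 16.2, and absolute power would be higher if more patients were analysed), and on baseline acting through a single continuous term.

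**What to change.** In 16.11, before unblinding, make the primary comparison the treatment effect from a Cox model (Efron ties) with continuous baseline PQL total as covariate, tested two-sided at 0.05. Attach the rule for further study to that test. State that its hazard ratio is conditional on baseline PQL. Keep the unadjusted log-rank and the Kaplan-Meier curves as the sensitivity and descriptive analysis. Check the size of the adjusted test by simulation at 35 per arm before fixing the wording.

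Continuous adjustment is preferable to stratifying by baseline tertile: it is more powerful once there is an association (94% against 90% at correlation 0.7) and costs less when there is none (about 1 point against 3).

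The change needs no new data or patients. It excludes nobody further, since a patient without a baseline score cannot be classified for the event in any case. The price is about 1 point of power if baseline is unrelated to time to improvement, and a hazard ratio that is conditional rather than marginal.
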